8.5.2 Subgroup Analysis of Key Secondary Endpoints

The 4 key secondary endpoints will be summarized for the following subgroups:

- Number of prior biologic and targeted synthetic DMARDs (e.g., < 4 vs. \geq 4)
- Prior use of JAKi (Yes vs. No)
- RA disease activity at informed consent (DAS28-CRP \leq 5.1 vs. DAS28-CRP $>$ 5.1)
- Moderate-to-severe RA at Day 0 (< 4 TJC28 or < 4 SJC28 vs. \geq 4 TJC28 and \geq 4 SJC28)

8.6 Exploratory Secondary Endpoints

The exploratory secondary endpoints through Week 12 include:

- ACR50/70 response
- Component (TJC28, SJC28, Subject Pain, SGA, HAQ-DI, EGA, hsCRP) 20/50/70 response
- DAS28-CRP score change from baseline and LDA/remission
- CDAI score change from baseline, LDA/remission and MCID response
- Mean HAQ-DI score change from baseline
- RAMRIS bone erosion, osteitis, synovitis, and CARLOS score changes from baseline
- RAMRIS bone erosion progression (> 0.5) rate from baseline
- SF-36/PCS/MCS score change from baseline
- EQ-5D-5L score change from baseline and response
- Percent change in plasma biomarker concentrations (e.g., IL-1, SAA, MMP-3)

8.6.1 Definitions of Exploratory Secondary Endpoints

ACR50/70 response at Week 12

ACR50/70 response corresponds to 50% and 70% improvement at Week 12 from baseline on the day of informed consent, respectively, in TJC28 and SJC28 and 3 out of 5 ACR core measures and follows the same general and statistical analyses as for ACR20 (see Section 8.3.1).

Component 20/50/70 response

20/50/70 response for each component (TJC28, SJC28, Subject Pain, SGA, HAQ-DI, EGA, hsCRP) corresponds to 20, 50 and 70% improvement from baseline to Week 12, respectively (see Section 8.2), and follows the same general and statistical analyses as for ACR20 (see Section 8.3.1).

DAS28-CRP score change and LDA/remission

The Disease Activity Score (DAS) is a derived measurement of 4 components with differential weighting:

- TJC28
- SJC28
- hsCRP (mg/L)
- SGA

A total score ranges from 0 to 10 and is computed as follows:

$$\text{DAS28-CRP} = 0.56 * \text{sqrt}(\text{TJC28}) + 0.28 * \text{sqrt}(\text{SJC28}) + 0.36 * \text{ln}(\text{CRP}+1) + 0.014 * \text{SGA} + 0.96$$

If one of the components is missing at an individual assessment point, the DAS28-CRP value for that assessment will be set to missing. An alternative imputation method for missing components may be applied as described in Section 8.1.

The DAS28-CRP score corresponds to the current RA activity:

- 0 to < 2.6 Remission
- 2.6 to < 3.2 Low disease activity (LDA)
- 3.2 to \leq 5.1 Moderate activity
- > 5.1 High activity

If one of the components is missing at a given assessment point, no imputations will be done, and the DAS28-CRP value for that assessment will be set to missing.

CDAI LDA/remission and MCID response at Week 12

The Clinical Disease Activity Index (CDAI) is a composite score consisting of the sum of:

- SJC28
- TJC28
- SGA/10
- EGA/10

The CDAI score is calculated as follows and ranges from 0 to 76 with higher values representing higher disease activity:

- CDAI = TJC28 + SJC28 + SGA + EGA

The CDAI score corresponds to the current RA activity:

- 0 to \leq 2.8 Remission
- >2.8 to \leq 10 Low disease activity (LDA)
- >10 to \leq 22 Moderate activity
- >22 High activity

The MCID varies depending on RA activity at baseline:

- -12 for high activity
- -6 for moderate activity
- 1 for low activity

If one of the components is missing at a given assessment point, no imputations will be done, and the CDAI value for that assessment will be set to missing. An imputation method for missing components may be applied as described in Section 5.8.1.

HAQ-DI score change from baseline

Change from baseline on the day of informed consent to Week 12 in mean HAQ-DI score as determined by subjects (see Section 8.2.5).

RAMRIS score and progression at Week 12

RAMRIS is the standardized system for RA MRI scoring of 4 different types of joint pathologies in the wrist and the hand. A total score for each pathology is generated by the summation of individual joint/bone scores as follows:

- *Synovitis*. 8 joints each scored on a scale from 0 = normal to 3 = severe, resulting in a total score from 0 to 24.
- *Bone erosion*. 25 bones each scored on a scale from 0 to 10, resulting in a total score from 0 to 250. An increase of > 0.5 from baseline to Week 12 will represent disease progression.
- *Osteitis*. 25 bones scored on a scale from 0 to 3, resulting in a total score from 0 to 75.
- *CARLOS (cartilage loss)*. 25 joints each scored on a scale from 0 to 4, resulting in a total score from 0 to 100.

Subjects will undergo MRI at Screening (baseline) and Week 12, and the MRI images will be scored by independent centralized blinded readers. Scores for each bone/joint will be calculated as the average of the score provided by each of the two readers. If a RAMRIS score from one of the readers is missing, then the RAMRIS score from the other reader will be used. If the score was

missing for both readers at any given time point, the average score is considered missing. An imputation method for missing components may be applied as described in Section 5.8.1. A listing will be provided that presents change in total score from baseline by subject for each of the RAMRIS pathologies. The number of observations and the total score change mean, minimum, maximum and 95% confidence interval will be presented for the treatment and control groups in a table.

The smallest detectable change (SDC) will be calculated for each of the joint pathologies to assess whether a patient experienced a change beyond measurement error. The SDC is calculated as:

$$\pm 1.96 \times \text{SD}_{\Delta(\text{CHANGE SCORES})} / (\sqrt{2} \times \sqrt{k})$$

where CHANGE SCORE = change in RAMRIS total score between two timepoints, $\text{SD}_{\Delta(\text{CHANGESCORES})}$ represents the standard deviation of difference in change scores between the two readers, and k = the number of readers (Bruynesteyn et al., 2005).

In addition, subgroup analyses will be performed for subjects with and without baseline joint damage that is predictive of future progression (Gandjbakhch et al, 2014).

SF-36/PCS/MCS score change from baseline to Week 12

Health-related quality of life will be assessed using the subject-completed Medical Outcomes Study Short-Form 36 (SF-36), which is a generic health survey that contains 36 questions covering eight domains of health. The SF-36 yields an 8-scale profile of functional health and well-being scores as well as physical and mental component health summary scores. The version 2, 4-week recall questionnaire will be used. Recoding, calculations, and standardization will be done as recommended in the User's manual for the SF-36 (Mariush, 2011). Each of the 8 domain scores is the sum of some of the overall 36 item scores.

Domain scores will only be calculated if less than half of the item scores are missing. Missing item scores will be imputed as the mean of the other item scores within the same domain. If at least half of the item scores of a domain are missing, imputation will not be performed, and the domain will be set to missing. An imputation method for missing components may be applied as described in Section 5.8.1.

EQ-5D-5L response at Week 12

A standardized instrument for measuring general health status within the following 5 dimensions:

- Mobility
- Self-care
- Usual activities
- Pain/discomfort

- Anxiety/depression

Each dimension is scored on 5-point scale as:

- 1 = No problems
- 2 = Slight problems
- 3 = Moderate problems
- 4 = Severe problems
- 5 = Extreme problems/Unable

General health status is scored on a VAS (0 = poor to 100 = the best). An imputation method for missing components may be applied as described in Section **5.8.1**.

Reduction in the proportion of subjects with problems (moderate, severe or extreme) will represent improvement.

An EQ-5D summary index score can be derived by applying a formula that attached weights, or index values, to each of the levels in each dimension. The index is calculated by deducting the appropriate weights from the value for full health (i.e., 1). Value sets are country specific and can be obtained from the EuroQol website (EuroQol Research Foundation, 2023).

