	In addition, 2 global measures are derived: 
 • PCS or physical component summary • MCS or mental component summary
SGA	Subject's global assessment of their RA disease activity using a NRS from 0 (inactive) to 10 (very active).
Source data	All information in original records and certified copies of original records of clinical findings, observations, or other activities in a clinical trial necessary for the reconstruction and evaluation of the trial.
Source documents	Original documents, data, and records. Printed, optical, or electronic documents containing source data.
Stratification	Allocation of subjects into treatment groups based on a characteristic that may affect trial outcome.
Subject	An individual who participates in a clinical investigation.
Subject's pain assessment	Subject's assessment of their RA-related pain using a NRS from 0 (no pain) to 10 (worst pain imaginable).
TJC28 & SJC28	A standardized assessment examining a total of 28 joints for signs of swelling and tenderness or pain in the shoulder (2), elbow (2), wrist (2), knee (2), and fingers (2 in each finger and thumb knuckle and second finger joint, 10 per hand or 20 total).
Treatment to Open Label (TOL) population	Treatment subjects from ITT population who received active stimulation through Week 12, completed Week 12 assessments, continued to receive active stimulation during open-label follow-up, and for whom follow-up data are available.
UADE	Any serious adverse effect on health or safety or any life-threatening problem or death caused by, or associated with, a device, if that effect, problem, or death was not previously identified in nature, severity, or degree of incidence in the investigational plan or application, or any other unanticipated serious problem associated with a device that relates to the rights, safety, or welfare of subjects. [21 CFR 812]
USADE	Any serious adverse device effect which by its nature, incidence, severity or outcome has not been identified in the current version of the risk analysis report. [BS EN ISO 14155]
Use error	Act or omission of an act that results in a different medical device response than intended by the manufacturer or expected by the user. Use error includes slips, lapses, and mistakes. An unexpected physiological response of the subject does not in itself constitute a use error. [BS EN ISO 14155]
VNS	A medical treatment that involves delivering electrical impulses to the vagus nerve.

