8.2.2 SGA

Subjects will complete a global assessment of their RA disease activity using the subject's global assessment of disease activity (SGA) item, a numerical rating scale (NRS) from "0" (inactive) to "10" (very active).

No imputations for missing data will be done.

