8.2.4 EGA

The joint evaluator will complete the evaluator's global assessment of disease activity item (EGA) using a NRS from "0" (inactive) to "10" (very active).

No imputations for missing data will be done.

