[2] Difference in mean score change from baseline and one-sided p-value based on the Mixed-effect Model Repeated Measure model with PROC MIXED. Difference in proportions and one-sided p-value based on the Cochran-Mantel-Haenszel test. Stratification factors are inadequate response or loss of response to JAKi and RA disease

Treatment (N=xxx)	Control (N=xxx)
----------------------	--------------------

severity at Day 0 for Stage 1 subjects and RA disease severity at Day 0 and inadequate response or loss of response to ≥ 4 biological DMARDs with ≥ 2 mechanisms of action for Stage 2 subjects.

[3] MCID is -12 if starting in high disease (> 22), -6 if starting in moderate disease (10-22); and 1 if starting in low disease (< 10).CDAI ranges from 0 to 76 with higher values representing higher disease activity.

Reference: Listing 16.x.x.x

SOURCE: xxxxx SAS 9.4 {program location} {run date/time}}

Table 14.1.2.13
 RAMRIS
 (ITT Population)

Variable	Treatment (N=xxx)	Control (N=xxx)
RAMRIS Bone Erosion Score		
Screening (baseline)		
N [1]	xx (xx.x%)	xx (xx.x%)
Mean (SD)	xxx.x (xxx.xx)	xxx.x (xxx.xx)
Median	xxx.xx	xxx.xx
Min-Max	xxx.x – xxx.x	xxx.x – xxx.x
Week 12		
N [1]	xx (xx.x%)	xx (xx.x%)
Mean (SD)	xxx.x (xxx.xx)	xxx.x (xxx.xx)
Median	xxx.xx	xxx.xx
Min-Max	xxx.x – xxx.x	xxx.x – xxx.x
Change from baseline (SDC: x.xx)		
N [1]	xx (xx.x%)	xx (xx.x%)
Mean (SD)	xxx.x (xxx.xx)	xxx.x (xxx.xx)
Median	xxx.xx	xxx.xx
Min-Max	xxx.x – xxx.x	xxx.x – xxx.x
95% CI for difference [2]	(xx.x, xx.x)	(xx.x, xx.x)
p-value for difference [2]	0.xxx	0.xxx
Progression rate from baseline (> 0.5)		
N [1]	xx	xx
Yes	xx (xx.x%)	xx (xx.x%)
Difference [2]	xx.x%	xx.x%
95% CI for difference [2]	(xx.x, xx.x)	(xx.x, xx.x)
p-value for difference [2]	0.xxx	0.xxx
RAMRIS Osteitis Score		
Screening (baseline)		
N [1]	xx (xx.x%)	xx (xx.x%)
Mean (SD)	xxx.x (xxx.xx)	xxx.x (xxx.xx)

CONFIDENTIAL

May not be reproduced outside of SetPoint Medical without written permission from Document Control.

99 of 158

Variable	Treatment (N=xxx)	Control (N=xxx)
Median	xxx.xx	xxx.xx
Min-Max	xxx.x – xxx.x	xxx.x – xxx.x
Week 12		
N [1]	xx (xx.x%)	xx (xx.x%)
Mean (SD)	xxx.x (xxx.xx)	xxx.x (xxx.xx)
Median	xxx.xx	xxx.xx
Min-Max	xxx.x – xxx.x	xxx.x – xxx.x
Change from baseline (SDC: x.xx)		
N [1]	xx (xx.x%)	xx (xx.x%)
Mean (SD)	xxx.x (xxx.xx)	xxx.x (xxx.xx)
Median	xxx.xx	xxx.xx
Min-Max	xxx.x – xxx.x	xxx.x – xxx.x
95% CI for difference [2]	(xx.x, xx.x)	
p-value for difference [2]	0.xxx	
RAMRIS Synovitis Score		

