6.2.4 CDAI

The Clinical Disease Activity Index (CDAI) is a composite score consisting of the sum of:

- SJC28
- TJC28
- SGA/10
- EGA/10

The CDAI score is calculated as follows and ranges from 0 to 76 with higher values representing higher disease activity:

$$\text{CDAI} = \text{TJC28} + \text{SJC28} + \text{SGA} + \text{EGA}$$

The CDAI score corresponds to the current RA activity:

- 0 to ≤ 2.8 Remission
- >2.8 to ≤ 10 Low disease activity (LDA)
- >10 to ≤ 22 Moderate activity
- > 22 High activity

The MCID varies depending on RA activity at baseline:

- -12 for high activity
- -6 for moderate activity
- 1 for low activity

If one of the components is missing at a given assessment point, no imputations will be done, and the CDAI value for that assessment will be set to missing. An alternative imputation method for missing components may be applied as described in Section 6.1.1.

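### Both SAPs divide SGA and EGA by 10 in the CDAI component list although both are recorded on 0–10 (maximum 58, not the stated 76); the SGA scale behind the DAS28-CRP weight should also be confirmed

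*SAP*

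**What the plan says.** **Recorded scale.** Protocol Section 3 defines SGA as the subject's "global assessment of their RA disease activity using a NRS from 0 (inactive) to 10 (very active", and gives EGA a 0–10 scale as well. The primary SAP (CLP-004) repeats this in 8.2.2 for SGA ("SGA) item, a numerical rating scale (NRS) from" 0 to 10) and in 8.2.4 for EGA ("global assessment of disease activity item (EGA) using a NRS from" 0 to 10).

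**CDAI.** CLP-004 Section 8.6.1 and the long-term SAP (CLP-008) Section 6.2.4 each list the components as SJC28, TJC28, SGA/10 and EGA/10. Directly below, each gives "CDAI = TJC28 + SJC28 + SGA + EGA" and a score that "ranges from 0 to 76 with higher values representing higher disease activity". Protocol Section 3 has only the undivided equation with the same range. The footnote to Table 14.1.2.12 in CLP-004 Appendix B agrees: "CDAI ranges from 0 to 76 with higher values representing higher disease activity". CDAI is an exploratory endpoint (CLP-004 Section 8.6).

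**DAS28-CRP.** CLP-004 Section 8.6.1 states: "A total score ranges from 0 to 10 and is computed as follows". The formula ends "0.014 * \text{SGA} + 0.96". Protocol Section 3 and CLP-008 Section 6.2.2 give the same formula. The component list states the unit of hsCRP (mg/L) but repeats no scale for SGA, and no section converts SGA from one scale to another. CLP-004 Section 8.4.1 sends the key secondary DAS28-CRP MCID response to 8.6.1, and the EULAR response uses the same score.

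**The concern.** Within one SAP section, SGA is treated as if it were on two scales. Dividing by 10 makes sense only for a 0–100 score. The CDAI equation and range make sense only for a 0–10 score. A programmer who follows the list would give the two global assessments a combined maximum weight of 2 points instead of 20. CDAI low disease activity, remission and MCID response would then be wrong.

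The same ambiguity raises a fair question about the next use of SGA. The DAS28-CRP formula feeds two of the four Hochberg-controlled key secondary endpoints (good/moderate EULAR response and MCID response), the subgroup split at 5.1 (CLP-004 Sections 8.3.5 and 8.5.2), and low disease activity and remission. If the 0.014 weight was intended for a different scale, literal programming would score those endpoints differently from what was meant. CLP-004 Section 5.1 presents the analyses as prespecified, so the scale should be settled before anyone sees results by arm.

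**Working it through.** **Inputs.** TJC28 and SJC28 run 0–28 (CLP-004 8.2.1). SGA and EGA run 0–10 (8.2.2, 8.2.4). The CDAI cut-offs are 2.8, 10 and 22, and the DAS28-CRP weights are those in 8.6.1. The MCID is a fall of at least 1.2 (8.4.1). The subgroup cut is 5.1.

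**1. Reproduce the stated CDAI maximum.** Equation with 0–10 scores: 28 + 28 + 10 + 10 = 76. This matches.

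**2. Apply the component list to the same data.** 28 + 28 + 10/10 + 10/10 = 58. This does not match. The list gives 76 only if SGA and EGA run 0–100 (28 + 28 + 10 + 10). On that scale the undivided equation would give 28 + 28 + 100 + 100 = 256. No single scale satisfies both the list and the equation.

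**3. Effect of programming the list (hypothetical subject).** TJC28 5, SJC28 4, SGA 5, EGA 4. Equation: 5 + 4 + 5 + 4 = 18, moderate activity. List: 5 + 4 + 0.5 + 0.4 = 9.9, low disease activity.

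**4. Size of the SGA term in DAS28-CRP.** As recorded: 0.014 × 10 = 0.14 units, or 0.14/1.2 = 12% of the MCID. If SGA entered as 0–100: 0.014 × 100 = 1.40 units.

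**5. Does the stated 0–10 DAS28-CRP range settle the scale?** The minimum is 0.96 either way. With TJC28 = SJC28 = 28, maximum SGA and an assumed CRP of 100 mg/L, the maximum is 7.21 as written and 8.47 with SGA × 10. Both lie inside 0–10, so the range does not discriminate.

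**6. When would the MCID result depend on the scale?** Let J be the fall in score from joints and CRP alone, and let SGA fall by d points. The total fall is J + 0.014d as written, or J + 0.14d with SGA × 10. The two readings disagree when 1.2 − 0.14d ≤ J < 1.2 − 0.014d, a band 0.126d wide:
- d = 1: 1.06 ≤ J < 1.186
- d = 3: 0.78 ≤ J < 1.158
- d = 5: 0.50 ≤ J < 1.13

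If SGA rises by d points, the band is 1.2 + 0.014d ≤ J < 1.2 + 0.14d, and the disagreement runs the other way. If SGA does not change, the readings agree. For the 5.1 split at SGA 5, they disagree when the score without SGA is above 4.40 and at most 5.03.

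**7. Hypothetical subjects** (TJC28/SJC28/CRP/SGA, baseline to Week 12):

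| Subject | As written | SGA × 10 | What changes |
|---|---|---|---|
| A: 15/12/10/7 to 9/8/6/3 | 5.06 to 4.17, fall 0.89 | 5.94 to 4.55, fall 1.39 | MCID: no becomes yes; side of 5.1 at baseline |
| B: 20/16/15/7 to 14/12/10/6 | 5.68 to 4.97, fall 0.71 | 6.56 to 5.73, fall 0.83 | EULAR: moderate becomes none |
| C: 15/12/10/5 to 6/6/5/7 | 5.03 to 3.76, fall 1.27 | 5.66 to 4.64, fall 1.02 | MCID: yes becomes no; side of 5.1 at baseline |

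Individual results can therefore move in either direction.

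**The case against.** On CDAI, the equation is the computing instruction. It agrees with the range, the protocol definition and the table footnote, so a careful programmer would probably use it and the list would do no harm. That is plausible, but the programs are not shown and the list still contradicts the text around it.

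On DAS28-CRP, the opposing case is stronger and mostly stands. SGA is a defined term on a 0–10 scale. The formula is identical in all three places and gives one score per subject when read literally. No section calls for a conversion or leaves a choice of scale open. Both arms are scored alike, so no bias in favour of either is shown. The SGA/10 bullets are themselves the text in error, which makes them weak evidence about a different formula. The revision history's note of a change from VAS to NRS describes superseded text and says nothing about the weight.

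A reader might infer from all this that the DAS28-CRP formula is wrong, or that two key secondary endpoints are mis-scored. The documents do not support that: none of them says which SGA scale the 0.014 weight assumes. What remains is a reasonable request for confirmation, because the same section misstates the scale of the same variable a few lines later.

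**Conclusion.** Two conclusions, of different strength.

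- **Established:** the CDAI component lists in CLP-004 Section 8.6.1 and CLP-008 Section 6.2.4 are inconsistent with the recorded 0–10 scales and with the equation and range beside them (58 against 76). The consequence is limited to exploratory endpoints, and arises only if the list rather than the equation is programmed.
- **Open query:** the scale assumed by the DAS28-CRP weight. On the literal reading the formula stands. On a 0–100 reading, which is an assumption and not something the documents state, the SGA term would be ten times larger and some subjects would change category. The share of real subjects in the bands above cannot be derived from the documents. The effect on EULAR response is shown only by illustration B.

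Primary ACR20 and ACR20 from Day 0 do not depend on the scale, because they use percentage improvement. HAQ-DI response does not use SGA. Sample size, power and alpha are unaffected. The key secondary endpoints are tested only if the primary succeeds (CLP-004 Section 8.5). This is a correction and a clarification worth making, but it falls short of a must-fix defect.

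**What to change.** 1. Delete the division by 10 from the SGA and EGA bullets in CLP-004 Section 8.6.1 and CLP-008 Section 6.2.4, so that they match the equation and the 0–76 range.
2. Before unblinding, have the sponsor confirm which SGA scale the 0.014 weight assumes. State it beside the formula in Protocol Section 3, CLP-004 Section 8.6.1 and CLP-008 Section 6.2.2. If it is 0–10, one explanatory line is enough. If it is 0–100, the text must say that the recorded score is multiplied by 10 before it enters the formula.
3. Check the CDAI and DAS28-CRP programs against the corrected text.
4. If unblinding has already happened, report the DAS28-CRP endpoints under both scorings and say when the choice was made.

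The cost is two component lists, three formula lines and a program check. No new data are needed.

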Baseline	Information and values collected during Screening. The RA disease activity assessments that serve as the baseline assessments used for determination of the primary and key secondary efficacy endpoints must be performed on the day of informed consent.
CDAI	
The CDAI score is based on 4 items:
 
 • TJC28 • SJC28

Term	Definition
	
 SGA EGA 
The CDAI score is calculated as follows and ranges from 0 to 76:
 
 CDAI = TJC28 + SJC28 + SGA + EGA 
The CDAI score corresponds to the current RA activity:
 
 0 to \leq 2.8 Remission >2.8 to \leq 10 Low disease activity (LDA) >10 to \leq 22 Moderate disease activity > 22 High disease activity 
The MCID is a score reduction by 12 if starting in high activity, 6 if starting in moderate activity, and 1 if starting in low activity.

Control to Open Label (COL) population	Control subjects from ITT population who received non-active (sham) stimulation through Week 12, switched to active stimulation after completing Week 12 assessments, continued to receive active stimulation during open-label follow-up, and for whom follow-up data are available.
Crossover	The process of switching from an initially assigned treatment to the other treatment being studied.
DAS28-CRP	
The DAS28-CRP score is a composite index providing a measure of disease activity, comprising:
 
 TJC28 SJC28 SGA hsCRP (mg/L) 
A total score ranges from 0 to 10 and is computed as follows:
 $\text{DAS28-CRP} = 0.56 * \text{sqrt}(\text{TJC28}) + 0.28 * \text{sqrt}(\text{SJC28}) + 0.36 * \ln(\text{CRP}+1) + 0.014 * \text{SGA} + 0.96$ 
The DAS28-CRP score corresponds to the current RA activity:
 
 0 to $<$ 2.6 Remission 2.6 to $<$ 3.2 LDA 3.2 to \leq 5.1 Moderate activity > 5.1 High activity 
A DAS28-CRP score reduction by 1.2 represents the MCID.

Day 0 (randomization, initiation of stimulation)	
Scheduled study visit occurring 14 to 21 days after Implant Procedure during which subjects undergo the following study procedures in the order specified:
 
 Day 0 assessments Randomization Initiation of stimulation 
Subjects must receive final surgical clearance with an approval to initiate study treatment before proceeding to the Day 0 visit.

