Population Analysis	Subject ID	Visit	CDAI Score	LDA (>2.8 to \leq 10)	Remission (0 to \leq 2.8)	MCID from Baseline	MCID from Initiation of Stimulation
		Week 168					
		Week 180					
		Week 192					

Note: The MCID varies depending on RA disease activity at baseline (i.e., on the day of informed consent for TOL and at Week 12 for COL) or initiation of stimulation (TOL, COL): -12 for high activity (CDAI > 22), -6 for moderate activity (>10 to \leq 22), or 1 if low disease activity (>2.8 to \leq 10).

Note to programmer: Baseline on the day of informed consent for TOL and at Week 12 for COL.

SOURCE: xxxxx SAS 9.4 {program location} {run date/time}

Listing 16.8.2.7.6
DAS28-CRP

Population Analysis	Subject ID	Visit	DAS28-CRP Score	LDA (0.6 to < 3.2)	Remission (0 to < 2.6)	MCID from Baseline (-1.2)	MCID from Initiation of Stimulation (-1.2)	DAS28-CRP Good/Moderate EULAR Response
TOL								
	xx-xxxx	Baseline	xx	N	N	--	--	--
		Day 0	xx	N	N	N	--	N
		Week 12	xx	Y	N	Y	Y	Moderate
		Week 24	xx	Y	Y	Y	Y	Good
		Week 36						
		Week 48						
		Week 60						
		Week 72						
		Week 84						
		Week 96						
		Week 108						
		Week 120						
		Week 132						
		Week 144						
		Week 156						
		Week 168						
		Week 180						
		Week 192						
COL								
	xx-xxxx	Week 12	xx	N	N	--	--	--
		Week 24	xx	N	N	N	Y	N
		Week 36	xx	Y	N	Y	Y	Moderate
		Week 48	xx	Y	Y	Y	Y	Good
		Week 60						
		Week 72						
		Week 84						
		Week 96						
		Week 108						
		Week 120						
		Week 132						
		Week 144						

Week 156
Week 168
Week 180
Week 192

Note to programmer: Baseline on the day of informed consent for TOL and at Week 12 for COL.

SOURCE: xxxxx SAS 9.4 {program location} {run date/time}

Listing 16.8.2.7.7
HAQ-DI

Population Analysis	Subject ID	Visit	HAQ-DI Score	MCID from Baseline (-0.22)	MCID from Initiation of Stimulation
TOL	XX-XXXX	Baseline	XX	--	--
		Day 0	XX	N	--
		Week 12	XX	N	N
		Week 24	XX	Y	Y
		Week 36	XX	Y	Y
		Week 48			
		Week 60			
		Week 72			
		Week 84			
		Week 96			
		Week 108			
		Week 120			
		Week 132			
		Week 144			
		Week 156			
		Week 168			
		Week 180			
		Week 192			
COL	XX-XXXX	Week 12	XX	--	--
		Week 24	XX	N	N
		Week 36	XX	Y	Y
		Week 48	XX	Y	Y
		Week 60			
		Week 72			
		Week 84			
		Week 96			
		Week 108			
		Week 120			
		Week 132			
		Week 144			
		Week 156			

Population Analysis	Subject ID	Visit	HAQ-DI Score	MCID from Baseline (-0.22)	MCID from Initiation of Stimulation
		Week 168			
		Week 180			
		Week 192			

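### Both SAPs give the CDAI MCID as -12, -6 and an unsigned 1 without stating the response inequality, whereas the protocol defines all three as reductions

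*SAP*

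**What the plan says.** Protocol section 3 (Definitions of Terms, CDAI) sets the MCID as a "score reduction by 12 if starting in high activity, 6 if starting in moderate activity, and 1 if starting in low activity". One noun, reduction, governs all three numbers.

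The Week 12 SAP, section 8.6.1, lists the same thresholds as signed changes. A minus sign stands before "12 for high activity" and before "6 for moderate activity", but the third bullet is simply "1 for low activity". The same section says that the score "ranges from 0 to 76 with higher values representing higher disease activity". Footnote [3] of Table 14.1.2.12 in Appendix B repeats the pattern in running text: minus signs on the first two values, then "and 1 if starting in low disease (< 10".

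The long-term SAP (CLP-008), section 6.2.4, has the same three bullets with the same missing sign. The note under Listing 16.8.2.7.5 in its Appendix C again ends "or 1 if low disease activity", and there defines the band as above 2.8 up to 10.

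CDAI response is analysed at Week 12 with the CMH test (Week 12 SAP, section 8.6.2). In CLP-008 it is reported descriptively, both from baseline and from initiation of stimulation (Table 14.8.2.12).

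**The concern.** On a scale where lower is better, an unsigned 1 next to -12 and -6 reads as an increase of 1. A responder flag coded uniformly as change <= threshold would then count a low-activity starter with no change, or with a 1-point worsening, as having reached a clinically important improvement.

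Neither SAP contains a sentence that rules this out. For the other two MCID endpoints the Week 12 SAP (section 8.4.1) states the direction and the boundary in words: a reduction of at least 1.2 for DAS28-CRP and of at least 0.22 for HAQ-DI. CDAI has no such sentence. Two competent programmers could therefore produce different CDAI responder rates from the same plan. The rates most exposed are uncontrolled open-label rates, where no comparison arm would reveal that stability was being counted as benefit.

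**Working it through.** **1. The four places against the protocol**

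| Place | High | Moderate | Low | Inequality stated? |
|---|---|---|---|---|
| Protocol section 3 | reduction of 12 | reduction of 6 | reduction of 1 | n/a (worded as a reduction) |
| Week 12 SAP 8.6.1 | -12 | -6 | 1 | no |
| Week 12 SAP, Table 14.1.2.12 footnote [3] | -12 | -6 | 1 | no |
| CLP-008 6.2.4 | -12 | -6 | 1 | no |
| CLP-008, Listing 16.8.2.7.5 note | -12 | -6 | 1 | no |

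Two of the four SAP entries are running text, so a list bullet lost in PDF reading does not explain the missing sign.

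**2. What each reading does to a low-activity starter**

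| Change in CDAI | Magnitude (change <= -1) | Signed, uniform (change <= +1) | Literal rise (change >= +1) |
|---|---|---|---|
| -1 | responder | responder | no |
| 0 | no | responder | no |
| +1 | no | responder | responder |
| +2 | no | no | responder |

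Only the first column agrees with the protocol. The first two columns differ only for changes above -1 and up to +1.

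**3. Who can start in low activity (above 2.8 to 10)**

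CDAI = TJC28 + SJC28 + SGA + EGA, maximum 28 + 28 + 10 + 10 = 76, as stated.

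*At consent.* Entry needs at least 4 tender and 4 swollen joints (Protocol 10.1), so CDAI >= 4 + 4 + 0 + 0 = 8. A score of 10 or less then requires the excess joints plus SGA plus EGA to total at most 2. There are 25 x 25 x 11 x 11 = 75,625 eligible integer combinations. Of these, 1 gives a score of 8, 4 give 9 and 10 give 10, so 15 are in low activity. This counts combinations, not patients, but it shows how narrow the opening is.

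*In CLP-008.* Baseline for the Control to Open Label (COL) population is Week 12. For the Treatment to Open Label (TOL) population, response is also computed from Day 0. Neither time point has a joint-count minimum. Randomization is stratified on fewer than 4 tender or fewer than 4 swollen joints at Day 0 (Protocol 17.1), so the plan itself expects subjects below the entry floor.

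**4. Illustrative size**

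The documents give neither an SD for CDAI change nor the share of COL in low activity at Week 12. Assume no true change and an integer change approximated by a normal distribution with mean 0 and SD s:

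- P(change <= -1) = Phi(-0.5/s)
- P(change <= +1) = Phi(1.5/s)

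| Assumed SD | change <= -1 | change <= +1 | Reclassified |
|---|---|---|---|
| 2 | 0.401 | 0.773 | 0.372 |
| 3 | 0.434 | 0.691 | 0.258 |
| 5 | 0.460 | 0.618 | 0.158 |
| 7 | 0.472 | 0.585 | 0.113 |

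For SD 2: Phi(-0.25) = 0.401, Phi(0.75) = 0.773, difference 0.372.

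The rise in the whole COL response rate is the low-activity share q times the last column, in percentage points:

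| q (assumed) | SD 2 | SD 3 | SD 5 | SD 7 |
|---|---|---|---|---|
| 10% | 3.7 | 2.6 | 1.6 | 1.1 |
| 20% | 7.4 | 5.2 | 3.2 | 2.3 |
| 30% | 11.2 | 7.7 | 4.7 | 3.4 |

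CDAI cannot fall below 0, so the symmetric normal is only a rough guide at the larger SDs.

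**The case against.** The SAPs print 1, not +1, and they state no rule of the form change <= threshold. Their MCID signs are loose elsewhere too: the HAQ-DI threshold appears as >= -0.22 in Table 14.1.2.2 and as >= 0.22 in Table 14.1.2.10, and DAS28-CRP appears as >= -1.2, which read literally would exclude larger improvements. In that setting, taking 1 as a magnitude is natural. The footnote wording also echoes the protocol's "6 if starting in moderate activity, and 1 if starting in low activity", where 1 is a reduction. Both SAPs are written under the protocol, and a programmer who checked it would find the right rule. CDAI score change, low disease activity and remission are reported separately and do not use the MCID.

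All of this stands, and it makes misclassification a possibility rather than a certainty. It does not remove the discrepancy, because the plan leaves the choice to the programmer.

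A reader might also infer that every COL subject with low disease at Week 12 would be misclassified at every long-term visit. The documents do not support that. Only changes above -1 and up to +1 are classified differently. Subjects starting in remission (2.8 or below) are outside the low-activity band. No low-activity share is given. COL includes only controls who continue active stimulation and have follow-up data, and missing visits stay missing (CLP-008 sections 5.2 and 5.5).

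**Conclusion.** The inconsistency is real and minor. The protocol requires a reduction of 1, both SAPs give an unsigned 1 after two negative values, and neither defines response by an inequality. Under one plausible coding, stable or slightly worse low-activity starters become responders; under another, the protocol is followed.

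The size depends on assumptions the documents cannot settle: 11 to 37 percentage points of low-activity starters for SDs of 7 down to 2 with no true change, and about 1 to 11 points of the COL response rate if 10-30% of COL start in low activity. TOL from Day 0 is exposed in the same way.

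A reader might infer a threat to the trial's efficacy conclusion. There is none: CDAI response is exploratory, the primary and key secondary endpoints do not use it, and the consent baseline leaves almost no low-activity starters in the Week 12 comparison.

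**What to change.** Write -1 for low activity in Week 12 SAP section 8.6.1, footnote [3] of Table 14.1.2.12, CLP-008 section 6.2.4 and the note to Listing 16.8.2.7.5. Add one sentence to section 8.6.1 and to CLP-008 section 6.2.4: CDAI MCID response is a change from baseline less than or equal to the MCID for the subject's starting activity category. The sign alone is not enough, because without the inequality the direction is still left to the programmer. In CLP-008 the sentence should also cover the analysis from initiation of stimulation. It is also the place to say how subjects starting in remission are handled, since no document gives an MCID for them.

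The cost is four characters and two sentences. No design feature, sample size or data collection changes.
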